Government agency regulation and directives require all study documentation pertaining to the conduct of a clinical trial must be retained by the investigator for at least 2 years after the last approval of a marketing application in an International Conference on Harmonization (ICH) region or at least 2 years have elapsed since the formal discontinuation of clinical development of the investigational product. The investigator will maintain all study documentation on file in a secure and safe location. Clinvest will notify the investigator in writing when retention is no longer necessary. No study records will be destroyed without prior agreement between Pharmalyte Solutions LLC and Clinvest.

INSTITUTIONAL REVIEW BOARD

Clinvest is responsible for obtaining IRB approval of the protocol, informed consent document, written information provided to the subject, recruiting material, and all other appropriate documents. The trial will not be initiated until IRB approval of all trial documents. The investigator will provide Pharmalyte Solutions LLC with documentation that the IRB has approved the protocol, informed consent, and any study-related materials to be provided to the subject before the study begins. In the event an amendment is needed to any document, Clinvest will also be responsible for the approval of all subsequent major changes. The investigator is responsible for obtaining initial and continuing review (annually if necessary) of the study by an IRB. Written approval must be forwarded to Clinvest before clinical supplies will be shipped. For continuing studies, written approval from the IRB must be sent to Clinvest at intervals not to exceed 1 year. All other appropriate reports on the progress of the study will be made to the IRB and the Sponsor by Clinvest in accordance with applicable governmental regulations and in agreement with the policy established by the Sponsor and the IRB.

TRAINING

Each approved study site will participate in a protocol training program prior to enrollment of any subjects in the study. The program must be attended by the principal investigator at the site, and at least one research coordinator, including the coordinator who will have the lead responsibility for coordination of the study at the site.

Comprehensive training will be provided by Clinvest to site personnel. Training topics will include protocol, study design, study documents, electronic data capture system, reporting of AEs and pregnancy, and any other study related tasks.

SAFETY MEASURES

Adverse Events

Adverse events (AEs) will be monitored throughout the study. All reported AEs will be documented on the appropriate eCRF.

Physical Examination

At screening and study exit, the investigator will examine the patient for any detectable abnormalities of the following body systems: general appearance; neck (including thyroid); head, eyes, ears, nose, and throat; lungs; heart/cardiovascular; abdomen; neurologic; extremities; back; musculoskeletal; lymphatic; skin; and other. The neurologic examination should be conducted to detect the presence of any significant sensory/motor abnormalities. A digital rectal examination is not required. Gynecological examinations are not required.

Weight should be measured at screening, day 1, and each subsequent office visit using the same scale for all patients at a given investigator site when possible.

Pregnancy tests for all females of childbearing potential. Urine pregnancy testing will be conducted at screening, on day 1, and each subsequent office visit to confirm continued non-pregnant status prior to study drug administration or study completion.

Clinical Laboratory Tests

Blood samples will be collected for clinical laboratory testing at Visits 2-5 for all patients qualifying for randomization. Non-fasting blood samples (approximately 10 mL for Electrolytes, Creatinine, and Ionized Magnesium) should be collected using standard laboratory instructions and procedures provided by the laboratories.

Vital Signs

Vital signs will be measured at screening, day 1, and each subsequent office visit. Systolic and diastolic blood pressure and pulse rate over 30 seconds should be taken after patients have been at rest (seated) for at least 2 minutes. Blood pressure should be recorded in mmHg. Pulse rate should be measured in beats per minutes.

Columbia Suicide Severity Rating Scale (C-SSRS)

The C-SSRS will be conducted at the screening visit and each subsequent office visit. The C-SSRS is a semi-structured interview designed to assess the severity and intensity of suicidal ideation, suicidal behavior, and non-suicidal self-injurious behavior over a specified time period (e.g., prior year, since last visit). The measurement of suicidal ideation is based on 5 “yes” or “no” questions (plus a description if answered “yes”) arranged in order of increasing severity. If the patient answers “yes” to either question 1 or 2, the intensity of ideation will then be assessed in 5 additional questions relating to the frequency, duration,

controllability, deterrents, and reasons for the most severe ideation. Suicidal behavior is then assessed by asking further questions to categorize the behaviors into actual, aborted, and interrupted attempts; preparatory behavior; and non-suicidal self-injurious behavior. The interview is used in full only if the initial questions are positive; this assessment is completed at all scheduled clinic visits at which other clinical assessments are to be carried out.

If any item(s) on the C-SSRS are answered with “yes”, a clinician investigator must review patient’s responses in order to:

- a) at screening and baseline determine patient’s study eligibility and potential need for referral to a mental health professional AND
- b) during the study evaluate patient’s need for appropriate medical management such as referral to a mental health professional.

A significant risk of suicide is defined as a “yes” in answer to:

- a) questions 4 or 5 on the suicidal ideation section; OR
- b) any questions on any item in the suicidal behavior section.

This must be reported as a serious adverse event and followed up accordingly. Additionally, if a patient responds “yes” to any of the suicidal ideation questions 1 to 3, a clinician investigator should apply clinical judgment to determine the need for reporting as an adverse event or serious adverse event and the need for any referral.

SUMMARY OF METHODS OF DATA COLLECTION

Data required for the evaluation of the primary and some secondary measures will be recorded by subjects using a daily e-diary. The following data will be collected daily with the e-diary (subject instructions and training for completion of the e-diary will be provided):

- Estimated total duration of headache that day (if no headache, subject will report 0 hours)
- Severity of headache at the time of onset (mild, moderate, or severe) only for subjects who report a headache duration > 0)
- Acute headache pain medication(s) usage
- Study medication usage
- Unusual symptoms

Should a subject skip a day of e-diary entry, the subject will be able to provide the missing information for up to 1 calendar day. The e-diary should not be completed on the day of the office visit; the last e-diary entry for the preceding period should be completed the day prior to the office visit.

Questionnaire data required to be directly collected from subject will be obtained at each appropriate visit using an electronic device as defined in the protocol. Questionnaires are to be completed by the subject and the answers to the questions on the questionnaires should come from the subject directly, not from family, friends, or the study support personnel.

Questionnaire data required to be collected directly from clinicians will be obtained at the appropriate visit and recorded in the eCRF per protocol.

STATISTICAL ANALYSIS

Subjects will be randomized 1:1 into the treatment groups. Randomization will not include any type of stratification.

An alpha of .05 will be used for statistical significance. All statistical tests will be two-sided. All data will be analyzed using JMP (SAS Institute, Inc.).

Descriptive statistics will establish baseline characteristics and adverse event frequency. Data for the primary endpoint will be statistically analyzed via a repeated measures ANCOVA controlling for ionized serum Mg levels. Data for each of the secondary outcome measures will be statistically analyzed for both within and between group changes via a 2-tailed Repeated Measures ANOVA and/or independent or dependent t-tests as appropriate. All ANOVAs will be followed by univariate post-hoc tests as appropriate. Multiple comparison adjustments will be made if needed.

An interim analysis will be performed when approximately 60 subjects have completed the study. The results of the interim analysis may lead to stopping the study for safety or futility. The interim analysis will not lead to stopping the study for efficacy. Only the primary endpoint and first secondary endpoint of migraine and headache day reduction will be assessed at the time of the interim analysis, as well as adverse events for safety purposes.

Modified Intent-to-Treat Population (mITT)

The modified intent-to-treat (mITT) population will include all randomized subjects who received at least one dose of study drug and obtained at least one endpoint measurement (mean change from baseline in the number of hours with headaches) after treating. The mITT population will be used for efficacy analyses.

Safety Population

The safety population will include all randomized subjects who received at least one dose of study drug (active or placebo).

A last observation carried forward (LOCF) method will be utilized to impute missing values for subjects continuing in the study, but missing values for this analysis. This type of imputation replaces the missing value with the last observation value obtained. Baseline observation carried forward (BOCF) method will be used if a subject discontinues the study. Thus, if a subject has a missing value at month 2 due to discontinuation, the baseline value will be utilized and the subject will be considered a non-responder.

PRIMARY ENDPOINT

To compare the mean change from baseline in the frequency of migraine headache days per 28-day period ending with the cessation of treatment period month 3 in subjects treated with MLD10 versus placebo.

A migraine headache day will be defined as a calendar day (00:00 to 23:59) with 4 or more hours of migraine headache, fulfilling ICHD-3 beta criteria, and/or any headache of any duration with the use of migraine-specific acute medications(s) (i.e. ergot alkaloids, ergot combinations, opioids, triptans, combination analgesics [simple analgesics combined with opioids or barbiturate with or without caffeine]).

SECONDARY ENDPOINTS

1. To compare change from baseline of subjects treated with MLD10 versus placebo on the following parameters during or after a 3 month treatment period:
 - the frequency of headache days
 - the average headache duration after 1, 2, and 3 months of treatment
 - reduction of pain severity at the time of headache onset
 - the use of acute medications after 1, 2, and 3 months of treatment
 - Migraine Disability Assessment Scale (MIDAS) scores at Visits 2 and 5
 - Subject Global Impression of Change (SGIC) at Visit 5
 - Physician Global Impression of Change (PGIC) at Visit 5
2. To assess the safety and tolerability of magnesium-L-lacate-dihydrate versus placebo in migraine headache subjects through the comparison of adverse events.

EXPLORATORY ENDPOINTS

To compare the change from baseline of subjects treating with MLD10 versus placebo on the following parameters during a 3 month treatment period.

- migraine with aura days
- serum ionized magnesium

SAFETY ENDPOINTS

Safety assessments will include:

- adverse events

COLLECTION AND DERIVATION OF ENDPOINTS

Data required for the evaluation of endpoints will be recorded for the duration of the study using electronic data capture and included subject and clinician reported outcomes.

Following visit 2, subsequent visits will occur every 28 days for 3 months. However, in practice, there may or may not be an exact 28-day duration between 2 consecutive visits. For data analysis purposes, the number of migraine headache days during the first 28 continuous days of the run-in period will serve as the “baseline” for calculating change from baseline for 28-day periods subsequent to each office visit. If the run-in period (starting with the screening visit and preceding the day before visit 2) exceeds 28 days, the run-in period will include the last 28-days. In order to be randomized, a subject must meet 80% diary completion compliance (22 days recorded unless otherwise approved by the Sponsor and/or Clinvest).

Primary Efficacy Variable

The primary efficacy variable is the mean change from baseline in the frequency of migraine headache days per 28-day period ending with the cessation of treatment period month 3 in subjects treated with MLD10 versus placebo. This variable is derived from

the e-diary. It is based on the count of days with migraine headaches, fulfilling ICHD-3 beta criteria, and/or headaches of any duration with the use of migraine-specific acute headache medication(s). The primary time point is treatment month 3, encompassing the last 28-day period before study end.

Secondary Efficacy Variables

- Change from baseline in the frequency of headache days per 28-day period. This variable will be derived from daily e-diary reports. It will be based on the count of days with headaches.
- Change from baseline in the total cumulative hours of headache per 28-day period. This variable will be derived from daily e-diary reports. It will be based on the sum of total headache duration for days with any headache.
- Change from baseline in the average pain severity at time of onset compared to each 28-day period. This variable will be derived from the daily e-diary reports.
- Reduction from baseline in the total number of acute headache pain medications used. This variable will be derived from the daily e-diary reports.
- Change from baseline in the total MIDAS score. This variable will be derived from the subject questionnaire.
- SGIC score at the end of treatment. This variable will be derived from the subject questionnaire.
- PGIC score at the end of treatment. This variable will be derived from the clinician reports.

APPENDIX 1
Proposed Revised International Headache Society Criteria for
Migraine Without and With Aura

Headache Classification Committee: J Olesen, et al. The International Classification of Headache Disorders, 3rd edition (beta version). *Cephalalgia*. 2013, 33:629-808.

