To compare the change from baseline of subjects treating with MLD10 versus placebo on the following parameters during a 3 month treatment period.

- migraine with aura days
- serum ionized magnesium

SAFETY OBJECTIVES

Safety assessments will include monitoring the parameters during the length of the study.

- adverse events
- physical examination
- urine pregnancy tests for all females of childbearing potential

- vital signs including blood pressure, pulse rate, and weight
- Columbia-Suicide Severity Rating Scale (C-SSRS)
- concomitant medications
- clinical chemistry measurements

SUBJECT SELECTION

Approximately 142 subjects will be randomized from the clinic and general population with a history of mild to severe migraine, with or without aura, that meets the International Classification of Headache Disorders (ICHD-3 beta) definition for episodic migraine with a frequency of 3-14 days of migraine (or headache treated with migraine specific medication) per month. Subjects will have a stable history of headaches meeting the above parameters for at least 3 months prior to enrollment. Subjects on migraine preventative medications will be required to be on a stable regimen for 30 days prior to and throughout the study period.

POWER ANALYSIS

A power analysis, using GPower Version 3.1.7, indicated a total sample size of 128 subjects would be needed to detect medium effects ($d = .25$) with 80% power using an analysis of covariance (ANCOVA) test to include fixed effects, main effects, and interactions with alpha being .05. Given an estimated 10% early termination rate, a total estimated sample size of 142 subjects is needed.

INCLUSION CRITERIA

Subjects must meet the following inclusion criteria:

1. male or female, in otherwise good health, 18 to 65 years of age.
2. history of frequent episodic migraine (3-14 migraine days per month) (with or without aura) according to the ICHD-3 beta for at least 3 months.
3. onset of migraine before age 50.
4. stable history of migraine at least 3 months prior to screening.
5. not currently taking a migraine preventive or has been taking preventive for at least 30 days prior to screening and agrees to not start, stop, or change medication and/or dosage during the study period.
6. if female of childbearing potential, has a negative urine pregnancy test at Visits 1-5 and uses, or agrees to use, for the duration of the study, a medically acceptable form of contraception as listed:

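### The power statement labels the detectable effect d = .25, but 128 subjects give 80% power only for f = .25, which is d = .50; at d = .25 power is about 29%

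*Protocol*

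**What the plan says.** The sample size rests on one short paragraph, Power Analysis. It opens "A power analysis, using GPower Version 3.1.7" and says that "128 subjects would be needed to detect medium effects ($d = .25$) with 80% power". The test is described as "using an analysis of covariance (ANCOVA) test to include fixed effects, main effects, and interactions with alpha being .05". The allowance for dropout follows: "Given an estimated 10% early termination rate, a total estimated sample size of 142 subjects is needed".

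The Statistical Analysis section supplies the rest of the design: "Subjects will be randomized 1:1 into the treatment groups" and "All statistical tests will be two-sided". It plans the primary analysis as a "repeated measures ANCOVA controlling for ionized serum Mg levels". Under Primary Efficacy Variable the protocol adds: "The primary time point is treatment month 3, encompassing the last 28-day period before study end".

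The protocol gives no target difference in migraine days, no standard deviation, and no correlation between covariate and outcome or between months. Nothing else in it ties the .25 to another scale or corrects the label.

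**The concern.** In the usual notation, d is the difference between two means divided by the SD, and f is the effect size of the ANOVA and ANCOVA F test. For two equal groups f = d/2. A value of .25 is a medium effect on the f scale; the medium effect on the d scale is .50. The protocol names an F test, calls the effect medium, and writes d.

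The choice of letter changes the claimed sensitivity by a factor of two. As written, the trial can detect a quarter-SD difference; as calculated, it can detect a half-SD difference. A null result would then be over-read as evidence against effects that the trial had little chance of seeing.

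There is also a possible effect on the interim look at about 60 completers, which may stop the study for futility. The protocol does not say how futility will be judged. If the calculation uses the design effect, the only documented value is d = .25. That would understate conditional power relative to the effect planned for, and so favour stopping.

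**Working it through.** **Inputs** (Protocol, Power Analysis and Statistical Analysis): N = 128, two arms 1:1, two-sided alpha .05, 80% power, ANCOVA F test, 10% early termination. The protocol does not state the numerator degrees of freedom. I take 1, which is the contrast between two arms.

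**Formulas.**
- Power = P(F' > F_crit), where F' is noncentral F with df1 = 1, df2 = N − 2 − (number of covariates) and noncentrality λ = f²N.
- For two equal groups, f = d/2.

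**1. Reproducing the protocol's 128, reading .25 as f.**
- λ = 0.25² × 128 = 8.0.
- Power is 79.8% at N = 127 and 80.1% at N = 128, so 128 is the first N to reach 80%.
- The result is 128 with 0, 1 or 2 covariates.
- The two-sample noncentral t test at d = .50 with 64 per arm also gives 80.1%.
- Solving for the smallest d with 80% power at 64 per arm gives 0.499.

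**2. Dropout step.** 128 / (1 − 0.10) = 142.2, so 142 reproduces.

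**3. Reading .25 as d, as written.** Then f = 0.125.

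| Quantity | d = .25 (f = .125) | d = .50 (f = .25) |
|---|---|---|
| λ at N = 128 | 0.125² × 128 = 2.0 | 8.0 |
| Power, 128 subjects | 28.9% | 80.1% |
| Power, 142 subjects | 31.6% | 84.1% |
| N for 80% power, noncentral F | 505 | 128 |
| Per arm for 80% power, noncentral t | 253 | 64 |

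The normal approximation agrees: 252 per arm at d = .25 and 63 per arm at d = .50.

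**4. Other readings that might rescue d = .25.**
- *One-sided test at d = .25:* 198 per arm (396 in total) by the normal approximation, which is not 128.
- *More numerator degrees of freedom at f = .25:* 158 for df 2 and 179 for df 3.
- *One-sample or paired t test with d = .25:* this also gives 128, but it is neither the named test nor a comparison of two parallel arms.
- *d on the unadjusted SD scale, with ANCOVA removing covariate variance* (effective d = .25/√(1 − ρ²)): power at N = 128 is 36.7% for ρ = .5, 50.2% for ρ = .7 and 80.1% only for ρ = .866.
- *Mean of three monthly values* (f multiplied by √(3/(1 + 2r))): power is 68.1% at within-subject correlation r = 0 and 34.8% at r = .7. With four values, 80% is reached only at r = 0.
- *Group-by-time interaction in a repeated-measures procedure, three values, f = .125:* power runs from 57.9% (r = 0) to 98.4% (r = .7). This can exceed 80%, but it is a different procedure with a different effect definition, and it needs a correlation that the power statement does not give.

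**The case against.** The strongest reply is that this is a slip of notation in an otherwise correct calculation. Both 128 and 142 reproduce, the word medium points to d = .50, and a statistician who sees GPower, ANCOVA and 128 together can recover what was meant. On this view 29% is the power for an effect that nobody planned for and should not be presented as a shortfall. It also depends on scaling d by the residual SD at a single time point, whereas the primary analysis is a repeated-measures model. The futility consequence concerns a rule that the protocol does not contain, and the request for migraine days and an SD goes beyond correcting a letter.

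Much of this stands. The trial is not undersized for a medium effect. The 29% shows that the label cannot be literal; it is not the power of the trial for its intended effect. The futility harm arises only if a calculation uses the stated d.

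Two parts do not carry. Repeated measurement does not rescue the statement, because the power paragraph names the ordinary ANCOVA, gives no correlation, and the primary time point is month 3. And the fact that a specialist could infer the intended value does not make a false statement of detectable effect harmless in the only place where the protocol states one.

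**Conclusion.** The concern holds. The protocol's 128 follows exactly from f = .25 and cannot follow from d = .25 under the test it names. The stated standardized difference is half of the one the trial is powered for.

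At d = .25 the trial would miss a true effect about 71% of the time with 128 subjects (100% − 28.9%), against a stated 20%. At d = .50 the stated power is correct.

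These figures assume two equal arms, one numerator degree of freedom, two-sided alpha .05, and d measured in residual SD units at a single time point. That is the scale of the named procedure and fits the month 3 primary time point. That f was the value entered is an inference, but a strong one, since it returns 128 to the exact integer.

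**What to change.** In Power Analysis, replace the effect size by Cohen's f = .25, equivalent to d = .50 for two equal arms, and state the numerator degrees of freedom (1). Leave 128 and 142 unchanged.

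Add the difference in migraine days per 28 days that this represents, 0.50 × the assumed SD, and state that SD. This goes a little beyond the bare correction, but it lets a clinical reader judge the target and would expose any later confusion of scale.

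If a futility calculation uses a design effect, carry d = .50 into it.

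The cost is one corrected line and a less flattering statement of sensitivity. No extra subjects are needed, and nothing changes in randomization, conduct or the main analysis.
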